13.4.2 Direct Access to Source Data/Documents

Qualified individuals designated by Dynavax or its representative will monitor all aspects of the study at regular intervals throughout the study and following study completion. This monitoring is for the purpose of verifying adherence to the protocol including appropriate storage of study treatment, completeness and exactness of the data being entered onto the CRFs, and compliance with FDA or other regulatory agency regulations. The investigator and investigator's institution agree to allow these monitors access to all study records, CRFs, and corresponding portions of the subject's clinical study files; to allow access to the clinical supplies, dispensing, and storage areas; and if requested, to assist the monitors. The investigator further agrees to permit direct access to source data/documents for study-related monitoring, audits, IRB review, and regulatory inspection(s).

In certain circumstances, a secondary audit may be conducted by members of Dynavax's Clinical Quality Assurance group or by Dynavax's designated representative. The investigator will be notified if this is to take place and advised as to the nature of the audit.

13.5 Case Report Forms

Case report forms (CRFs) will be used at the clinical study site to collect study data for enrolled subjects. For screen failures, the sponsor will collect, at a minimum, age, sex, ethnicity, race, the reason for screen failure and any SAEs that occur during the screening period.

When data are available, authorized clinical study site personnel will carefully and accurately record the data on the CRFs. Sites must ensure that all source documents are maintained according to ICH/GCP guidance and support the data that are entered onto the CRFs.

Case report forms will be in electronic form (eCRFs) for this study. The eCRF data will be captured in a system validated according to procedures that comply with 21 CFR Part 11, and ICH Guidelines for GCP E6 (R2), November 2016, Section 5.5. The eCRFs will be reviewed and signed by the principal investigator or someone clinically qualified and identified on the delegation log as someone that can sign-off on the eCRF.

13.6 Data Handling

The sponsor may designate a Contract Research Organization (CRO) to perform data management. The CRO will write a data management plan outlining the data management systems, procedures, and agreements between the CRO and sponsor. The plan will be reviewed and signed by a representative of the sponsor's data management department.

Outside the electronic data capture (EDC) system, when appropriate, the sponsor or designee (CRO) will receive FDA 21 CFR Part 11 (or locally required equivalent) compliant external lab data transfers from a validated laboratory information management system and subject reported safety information from a validated electronic patient report outcome (ePRO) system.

After database lock, the investigator will receive a copy of the subject data for archiving at the study site.

Validation checks will be conducted to capture data errors, and data clarification queries will be generated at the time of data monitoring. Validation checks and queries will be issued to the investigational site for resolution, and the database will be updated to reflect query resolutions as appropriate.

Data verification against the source documents will be performed by the sponsor or its designee prior to locking of the study database. Following the completion of source data verification, a thorough review of data will be completed manually by the clinical data managers to ensure data consistency and to identify and request correction of any remaining data errors. All queries will be resolved or closed with written documentation providing reasons for irresolvable queries. Additional manual validation checks will be performed as needed.

13.7 Coding of Adverse Events, Drugs, and Diseases

AEs and medical histories will be coded using a current version of the MedDRA. Prior and concomitant medications will be coded according to the World Health Organization Drug Dictionary.

13.8 Record Retention

The investigator must retain all records relating to the conduct of this study (including subject's study records, receipt and disposition of all investigational materials, subject exclusion logs, signed consent forms, eCRFs, all correspondence, and other supporting documentation) for at least 2 years after a marketing application for this indication is approved; or if an application is not filed or not approved for the drug for this indication, for at least 2 years after clinical development for the drug has been formally discontinued and the appropriate regulatory or health authorities have been notified. However, in certain instances, documents may need to be retained for a longer period if required by regulatory requirements or by an agreement with Dynavax.

The investigator may withdraw from the responsibility of retaining records only after transferring custody of the records to another individual who will accept responsibility for them. A written notice of transfer must be provided to Dynavax prior to or no later than 10 days after transfer.

The investigator must allow representatives of the FDA, the governing IRB, or other regulatory agencies to inspect all study records. If informed of such an inspection, the investigator will notify Dynavax within 24 hours of being informed.

The investigator must obtain written approval from Dynavax prior to the destruction of any records relating to the conduct of this study.

14 USE OF INFORMATION AND PUBLICATION

No information related to data obtained and generated in this study shall be released or publicized without the prior written consent of an Agreements Officer Representative of the U.S. Government.

Any publication will have the following statement to acknowledge the support of the Government whenever publicizing the study in any media:

This project has been funded in part by the U.S. Government under Agreement W911QY-21-9-0018. The US Government is authorized to reproduce and distribute reprints for Governmental purposes notwithstanding any copyright notation thereon.

APPENDIX 1: SCHEDULE OF TRIAL EVENTS

	Screening ^a	Treat- ment	Follow up	Treat- ment	Follow up		Treat- ment	Follow up		EOS/ Early Discontinuation ^b (TC)
	Days									393 (± 14) (Early discontinuation: 28 days after last study vaccine)
	Weeks									13
Informed Consent	X									
Inclusion/Exclusion Criteria	X									
Demographics ^c	X									
Medical and Medication History ^c	X	X								
Vital Signs ^f	X	X			X		X			
Physical Exam ^g	X									
HIV, HBV, HCV Testing ^h	X									
Pregnancy test ⁱ	X				X		X			
Serum chemistry ^k	X				X	X				
Hematology ^l	X				X	X				
Blood sample for rF1V [REDACTED] concentration ^m			X		X ^d	X	X	X	X	
Blood samples for reserve/exploratory objectives ⁿ	X		X		X	X	X	X	X	
Study injections for rF1V vaccine and CpG 1018 ^o			X				X			
Study injections for rF1V vaccine and placebo ^o			X				X			
30-minute post-injection observation ^p			X				X			
Distribute and/or Review Subject e-Diary or equivalent) Instructions			X				X			
Review Subject e-Diary (or equivalent) with Daily Temperature and Local/Systemic Reactions ^j			X				X			
Assessment of AEs, SAEs, immune-mediated AESIs ^{q,r}	X ^r	X	X	X	X	X	X	X	X	X
Concomitant Medications		X	X	X	X	X	X	X	X	X

AE = adverse event; BP = blood pressure; CBC = complete blood count; HBV = hepatitis B virus; HCV = hepatitis C virus; HIV = human immunodeficiency virus; HR = heart rate; RR = respiratory rate; SAE = serious adverse event; TC= telephone call.

APPENDIX 1: SCHEDULE OF TRIAL EVENTS (CONT'D) FOOTNOTES

Screening ^a	Routine laboratory tests (serum chemistry, hematology) for screening should be performed within 28 days prior to enrollment. Subjects may have the screening window extended an additional 7-calendar days if they have equivocal laboratory results or if they cannot be enrolled during the screening window. The screening window may only be extended one time and must have prior approval by the sponsor's medical monitor.
EOS/Safety F/U ^b	A mandatory EOS/Safety Follow-up telephone call will be performed [32 days] [3] after the administration of the last study vaccine. If a subject receives less than 3 doses of vaccine, their EOS visit will be 28 days after their last dose. The EOS visit procedures will be performed as an Early Discontinuation visit if the subject is permanently discontinued early from the trial.
Telephone Call ^c	Telephone call Day 4 (Part 1 only) and EOS
Part 1 Final immunogenicity Assessment ^d	Part 1 final immunogenicity assessment will be conducted based on Day 57.
Demographics/Medical History/Prior Medications ^e	Demographic and baseline characteristics of sex, race, ethnicity, age, weight, and height, and medical history will be collected. Report complete medication history for 28 days prior to Baseline (Day 1).
Vital Signs ^f	Includes oral temperature (only at trial injection visits), heart rate, respiratory rate, systolic and diastolic blood pressure.
Physical Examination ^g	The investigator or qualified designee will conduct physical examinations. A complete physical examination is conducted at Screening. A symptom-directed physical exam is conducted at all other designated time points.
HIV, HBV, HCV Testing ^h	HIV, HBV, HCV testing.
Pregnancy Test ⁱ	For females of childbearing potential, a serum pregnancy test will be collected at screening and must be negative for the subject to participate. A urine pregnancy test must be negative within 24 hours prior to administration of each study vaccine. The test must be negative for the subject to receive study injection.
Subject Diary ^j	At the Day 1 visit, subjects are provided with a ruler, thermometer and instructions for completing the study diary. At Day [] subjects are instructed to complete the e-diary (or equivalent) to record any solicited local (pain, pruritus, redness, and swelling at the injection site) and solicited systemic signs and symptoms (fatigue, chills, myalgia, malaise, fever, gastrointestinal symptoms, and headache) during the 7-day follow-up period after administration of each study vaccine.
Serum Chemistry ^k	Chemistry (includes sodium, potassium, chloride, bicarbonate, BUN, Cr, glucose, calcium, AST, ALT, LDH, bilirubin, alkaline phosphatase).
Hematology ^l	Hematology includes red blood cell count, Hgb, hematocrit, WBC count with differential, and platelet count.
Serology ^m	Standardized enzyme-linked immunosorbent assays [] to determine serum concentrations of antibodies to rF1V. Samples will be drawn prior to study vaccine injection on vaccination days. The same sample will be used for the exploratory analysis to determine serum concentrations of antibodies to rF1 and rV.
Reserve Serum Aliquot ⁿ	An extra aliquot of serum collected and stored frozen for possible future testing (drawn prior to study injection on vaccine days)
Study Vaccine Administration ^o	Subjects will be randomly assigned and receive an injection of study vaccine on vaccination days. If Group 2 is selected from the Part 1, then in Part 2, placebo will not be co-administered with rF1V.
Post-Injection Observation ^p	Subjects will remain in the clinic for 30 minutes after administration of study vaccine for observation of post-injection local and systemic reactions and AEs.
Review AEs ^q	All AEs will be graded per CBER Toxicity Grading Scale for Healthy Adult and Adolescent Volunteers Enrolled in Preventive Vaccine Clinical Trials and evaluated for seriousness. AEs will be collected Day 1 through Week 56 or Early Discontinuation Visit.
Review SAEs ^r	All SAEs will be evaluated from the time the consent is signed through the EOS Visit. SAEs must be reported to Dynavax or its designee within 24 hours of the knowledge of the event.

APPENDIX 2: TOXICITY GRADING SCALE FOR HEALTHY ADULT AND ADOLESCENT VOLUNTEERS ENROLLED IN PREVENTIVE VACCINE CLINICAL TRIALS

	Mild (Grade 1)	Moderate (Grade 2)	Severe (Grade 3)	Potentially Life Threatening (Grade 4)
Local Injection Site) Reactions				
Pain	Does not interfere with activity	Repeated use of non-narcotic pain reliever > 24 hours or interferes with activity	Any use of narcotic pain reliever or prevents daily activity	Emergency room (ER) visit or hospitalization
Tenderness	Mild discomfort to touch	Discomfort with movement	Significant discomfort at rest	ER visit or hospitalization
Erythema/Redness ^a	2.5 – 5 cm	5.1 – 10 cm	> 10 cm	Necrosis or exfoliative dermatitis
Induration/Swelling ^b	2.5 – 5 cm and does not interfere with activity	5.1 – 10 cm or interferes with activity	> 10 cm or prevents daily activity	Necrosis
Pruritus ^c	No interference with activity	Some interference with activity, not requiring medical intervention	Prevents daily activity and requires medical intervention	ER visit or hospitalization
Systemic Reactions				
Fever (°C)	38.0 – 38.4	38.5-38.9	39.0-40	>40
Myalgia	No interference with activity	Some interference with activity	Significant: prevents daily activity	ER visit or hospitalization
Fatigue	No interference with activity	Some interference with activity	Significant: prevents daily activity	ER visit or hospitalization
Malaise	Uneasiness or lack of well being	Uneasiness or lack of well being; limiting instrumental ADL	A grade is not available	A grade is not available
Chills ^c	No interference with activity	Some interference with activity, not requiring medical intervention	Prevents daily activity and requires medical intervention	ER visit or hospitalization
Nausea/vomiting	No interference with activity or 1 – 2 episodes/24 hours	Some interference with activity or > 2 episodes/24 hours	Prevents daily activity, requires outpatient IV hydration	ER visit or hospitalization for hypotensive shock
Diarrhea	2 – 3 loose stools or < 400 gms/24 hours	4 – 5 stools or 400 – 800 gms/24 hours	6 or more watery stools or > 800gms/24 hours or requires outpatient IV hydration	ER visit or hospitalization

	Mild (Grade 1)	Moderate (Grade 2)	Severe (Grade 3)	Potentially Life Threatening (Grade 4)
Headache	No interference with activity	Repeated use of nonnarcotic pain reliever > 24 hours or some interference with activity	Significant; any use of narcotic pain reliever or prevents daily activity	ER visit or hospitalization
Systemic Illness				
Illness or clinical adverse event (as defined according to applicable regulations)	No interference with activity	Some interference with activity not requiring medical intervention	Prevents daily activity and requires medical intervention	ER visit or hospitalization

Source: ([Center for Biologics Evaluation and Research 2007](#)).

ER = emergency room; IV = intravenous.

^a In addition to grading the measured local reaction at the greatest single diameter, the measurement should be recorded as a continuous variable.

^b Induration/swelling should be evaluated and graded using the functional scale as well as the actual measurement

^c Not part of CBER grading scale.

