Group 3: 0.5 mL of rF1V vaccine and 0.25 mL of placebo will be administered intramuscularly in the same or nearby location of the deltoid muscle of the non-dominant arm on Days [REDACTED]
[REDACTED].

Scenario 2: Group 2 is selected.

Group 2: 0.75 mL of the bedside mix of rF1V vaccine and CpG 1018 will be administered intramuscularly in the deltoid muscle of the non-dominant arm on Days 1 [REDACTED]
[REDACTED].

Group 3: 0.5 mL of rF1V vaccine will be administered intramuscularly the deltoid muscle of the non-dominant arm on Days [REDACTED]
[REDACTED].

Safety Assessments	
All subjects will be monitored for safety through Day 393.
 
Safety assessments include the following:
 
 Assessment of post-injection local and systemic reaction (for 7 days post each injection) Adverse events assessments (AEs, SAEs, AESIs, deaths) Vital signs measurements Physical examinations
Stopping Rules	
Dosing of all subjects will be temporarily stopped for any of the following:
 
 Two or more subjects who experience Grade 3 (severe) or higher severity solicited adverse reactions (considered by the sponsor to be possibly or probably related to treatment) lasting more than 48 hours AND considered by the DMC to be clinically significant Two or more subjects who experience the same or similar grade 3 or higher unsolicited adverse event that is assessed as at least possibly related to the treatment Any Suspected Unexpected Serious Adverse Reaction (SUSAR) (considered by the Sponsor to be possibly or probably related to treatment) Any death or life-threatening SAE regardless of relationship to vaccine Any type 1 AMI 
Dosing may be resumed following review of available safety data by the DMC as specified in the DMC Charter.

Immunogenicity Assessments:	Immunogenicity assessments include Serum rF1V Bridge ELISA concentration as outlined in the summary of trial events

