- Grade 4 post-injection reaction (PIR) within 7 days after any study injection
- Clinically significant Grade 3 or higher systemic reaction (eg, angioedema, generalized urticaria) within 7 days after any study injection
- Grade 3 or 4 hypotension within 24 hours of any study injection
- Grade 3 or 4 respiratory reaction or symptoms occurring within 24 hours of any study injection
- Any life-threatening AE, regardless of relationship to study drug
- Any AMI
- Any confirmed immune-mediated AE
- Violation of protocol eligibility criteria
- Subject received prohibited medications
- SAE assessed as a suspected adverse reaction (SAR) or adverse reaction (AR)
- Subject becomes pregnant or begins breastfeeding

If the subject is not eligible for subsequent study injections, **the subject will not be withdrawn from the study**, but, if possible, will be followed for safety through End-of-Study (EOS) Visit.

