7.5 Concomitant Medications

7.5.1 Prohibited Treatments or Therapies

The following non-study medications are prohibited:

- **Any licensed COVID-19 vaccine or inactivated vaccine (including vaccines containing mRNA or CpG)**
 - :S 14 days prior to each study injection through 14 days after each study injection
- **Any live vaccine**
 - :S 28 days prior to each study injection through 28 days after each study injection

- **Other concomitant medications**

- :S 28 days prior to vaccine injection (Day 1) through 28 days after the third study vaccine injection Week 26 (Day 183):
 - Systemic corticosteroids (more than 3 consecutive days) or other immunomodulators or immunomodulators immune suppressive medication, with the exception of inhaled steroids
 - Any other investigational medicinal agent
- :S 90 days prior to vaccine injection (Day 1) and through 28 days after the third study vaccine injection Week 26 (Day 183):
 - Granulocyte or granulocyte-macrophage colony-stimulating factor
 - Immunoglobulins or any blood products
 - Antisense oligonucleotides
 - Drugs/investigational agents with very long half-lives (defined as 2' 60 days)
- At any time prior to vaccine injection (Day 1) and through 28 days after the third study vaccine injection Week 26 (Day 183):
 - DNA plasmids or other genetic therapy intended to integrate permanently into host cells

If a subject requires treatment that is prohibited, **the subject will not be withdrawn from the study** but will be followed for safety through Week 56.

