9.4.5 Adverse Events

All AEs, as defined in [Section 10.0](#), will be evaluated and reported from immediately after the study vaccine injection on Day 1 through EOS (Week 56 or Early Discontinuation) Visit. See the Schedule of Events ([Appendix 1](#)) for the AEs collection schedule.

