9.7 Early Discontinuation/End of Study

An EOS Assessment is required at Week 56 (Day 393) in alignment with the protocol, GCP as defined in International Council for Harmonisation (ICH) guidelines and US Code of Federal Regulations (CFR), and applicable local regulatory requirements. The EOS procedures will be performed as an Early Discontinuation assessment at least 28 days after the last study injection if the subject is permanently discontinued early from the trial. Investigators are responsible for monitoring the safety of subjects throughout the course of the study and for providing appropriate medical care. The investigator will perform all tasks directly or is responsible for overseeing and training qualified site personnel as delegated to perform study tasks. In addition, investigators are responsible for alerting Dynavax to any event that seems unusual and for reporting all AEs, SAEs, pregnancies, and deaths in the appropriate CRFs.

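### Appendix 1 footnote b ends follow-up 28 days after the last dose for anyone with fewer than three doses, while the rest of the protocol follows them to Week 56 (Day 393)

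*Protocol*

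**What the plan says.** Footnote b to the schedule of events (Protocol Appendix 1) states: "If a subject receives less than 3 doses of vaccine, their EOS visit will be 28 days after their last dose". The sentence after it covers subjects permanently discontinued from the trial and has the EOS procedures done as an Early Discontinuation visit.

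Other parts of the protocol set a different end point:

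- Synopsis, Safety Assessments: "All subjects will be monitored for safety through Day 393".
- Section 9.7 requires the EOS assessment at Week 56, Day 393. The only earlier route is for a subject permanently discontinued from the trial, and there 28 days is a minimum.
- Section 7.5.1: a subject who needs a prohibited treatment is not withdrawn "but will be followed for safety through Week 56".
- Section 5.3: a subject who can have no more injections stays in the study and, "if possible, will be followed for safety through End-of-Study (EOS) Visit".
- Section 9.4.5 collects adverse events "through EOS (Week 56 or Early Discontinuation) Visit". Footnote q of Appendix 1 agrees: "AEs will be collected Day 1 through Week 56 or Early Discontinuation Visit".
- The EOS column of the schedule gives Day 393 ± 14, with 28 days after the last vaccine for early discontinuation.

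In the SAP, section 6.1 runs the treatment-emergent period from first injection to the EOS visit without naming a day. Section 6.2 bases unsolicited-safety percentages on the number of subjects in the analysis population.

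**The concern.** The protocol separates stopping injections (5.3) from leaving the study (5.4, 9.7). Footnote b ignores that distinction and fixes EOS by dose count. A site working from the schedule of events could close a subject who stopped injections but stayed in, many months before the date the body of the protocol requires.

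What is at stake is the capture of late adverse events, SAEs and AESIs. Once EOS is recorded, collection stops under 9.4.5 and the SAP 6.1 window closes. The subject still counts in the denominator, so the reported percentages are lowered by follow-up that did not take place. Some of these subjects were stopped for a confirmed immune-mediated event, a myocardial infarction or a related SAE. Long observation matters most for them, and section 2.4.2 says there are no clinical data on CpG 1018 added to rF1V.

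**Working it through.** **Inputs**

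- Injection days 1, 29 and 183: Protocol 9.4.1.
- EOS at Week 56, Day 393, window ± 14 days: Protocol 9.7 and the Appendix 1 header.
- No Day 0; Day 1 is the first injection: SAP 6.1.
- Footnote b rule: EOS day = day of last dose + 28.

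**The plan's own figure.** Day = 7 × week + 1, so Week 56 is 7 × 56 + 1 = Day 393. Four weeks of screening plus 56 weeks gives the 60 weeks in section 4.2. Both reproduce. Planned follow-up is 393 − 1 = 392 days, and the EOS window is Day 393 − 14 = 379 to Day 393 + 14 = 407.

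**EOS under footnote b**

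| Injections received | EOS day | Days short of 393 | Days short across the window | Share of 392 days observed |
|---|---|---|---|---|
| One (Day 1) | 1 + 28 = 29 | 393 − 29 = 364 | 350 to 378 | 28/392 = 7.1% |
| Two (Days 1 and 29) | 29 + 28 = 57 | 393 − 57 = 336 | 322 to 350 | 56/392 = 14.3% |

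Neither date is near the window.

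**Where the rules collide**

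1. *Prohibited medication.* Section 5.3 stops dosing, section 7.5.1 requires follow-up to Week 56, and footnote b ends it at 28 days. A site cannot comply with both.
2. *Other stopping reasons.* Section 5.3 names no day, only EOS, so the date depends on which EOS rule the site applies: Day 393 under 9.7 and the synopsis, Day 29 or 57 under footnote b.
3. *Sections 9.4.5 and footnote q.* Both allow Week 56 or Early Discontinuation. A subject kept in under 5.3 has not discontinued early, so Week 56 applies. This conflict is indirect: it needs 5.3 to complete it.
4. *Timing.* If a subject with two injections has the stopping event after Day 57 and before Day 183, the footnote b EOS date has already passed.

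**Which events could be lost.** Section 5.3 lists 11 stopping reasons. Eight are clinical events, and three are not (eligibility violation, prohibited medication, pregnancy or breastfeeding). For the eight, the event that led to stopping is normally already recorded. SAP 8.7 counts a subject once per preferred term, once per system organ class and once overall, at worst severity, so only a later event in another row or a worse grade could be missed. For the three, a first adverse event could be missed.

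**Literal reach of the wording.** Section 11.2 describes Groups 1 and 2 as receiving two doses of study vaccine, so fewer than three doses of vaccine would literally include them: 20 + 20 in Part 1 plus 70 in Part 2 = 110 of about 200 (55%). This is probably not intended and the finding does not depend on it, but it shows that the sentence is loosely worded.

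**The case against.** The best defence is that footnote b annotates a column shared by EOS and Early Discontinuation, whose header already gives 28 days for early discontinuation. On that reading the disputed sentence only times the early visit and the next one gives its procedures. This may be what was meant, but the condition written is a dose count, and 5.3 creates subjects who meet it without leaving the study.

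Other points, and what stands of each:

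- *Sections 9.4.5, footnote q and the header all carry an early-discontinuation alternative.* True. The direct clashes are with 7.5.1, 9.7 and the synopsis.
- *Footnote b is not the only 28-day wording.* Sections 10.10.2 and 10.11 use it for unrelated SAEs and for breastfeeding, and 9.2 and 9.6 set a 28-day minimum. The first two are narrower rules, and a minimum conflicts with neither reading.
- *Safeguards exist.* Pregnancy is followed to outcome (10.11), and related SAEs are followed beyond EOS (9.4.5.1, 10.10.2). This reduces the loss. But following a known SAE does not capture a new event, and an event after a shortened EOS is still outside the SAP 6.1 window.
- *A Grade 4 post-injection reaction is not formally an adverse event unless it lasts beyond 7 days (10.2).* Correct. It is already captured as a reaction, so the argument is unchanged.
- *Groups 1 and 2 are not really covered.* Probably right: section 7.5.1 refers to a third injection without distinguishing groups, and 6.2.2.2 gives Group 2 a separate placebo injection.
- *The first sentence of footnote b also ties the EOS call to the last vaccine.* Its interval is unreadable in the public text, so nothing is built on it. A replacement sentence that states Day 393 settles the date.

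**Conclusion.** The concern holds. Footnote b contradicts sections 7.5.1 and 9.7 and the synopsis, and also 9.4.5 and footnote q once 5.3 keeps the subject in the study. The weight of the text shows that Week 56 is the intended rule and that footnote b departs from it.

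For an affected subject the loss is large: 364 or 336 of 392 days. At group level it is unknown, because the documents do not say how many subjects stop injections and stay in. With descriptive safety analyses it is probably small. The point rests on two assumptions: that a site follows footnote b literally, and that the subject remains in the study. It is worth correcting because it shortens safety follow-up and costs very little to put right, not because it threatens the primary immunogenicity conclusions.

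**What to change.** 1. Replace the disputed sentence in footnote b with: *Subjects who stop study injections but remain in the study have EOS at Day 393 (±14). The Early Discontinuation assessment is only for subjects who leave the study, and takes place no sooner than 28 days following their final study injection.* Referring to study injections also removes the literal reading that takes in Groups 1 and 2.
2. Optional: in SAP 8.1, add a disposition row giving, by group, the number of subjects with EOS before Day 393. If follow-up is already advanced, this row would show whether sites applied footnote b.
3. Optional and editorial: align the 28-day alternatives in sections 10.10.2 and 10.11.

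The cost is one protocol sentence and, if wanted, one table row. For each subject who stops injections early it adds the remaining adverse-event contacts and the Day 393 telephone call. It introduces no new policy.
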